8.4.4 Medication error

If a medication error occurs in the course of the study, then the Investigator or other site personnel informs the appropriate AstraZeneca representatives within 1 day i.e., immediately but no later than 24 hours of when he or she becomes aware of it.

The designated AstraZeneca representative works with the Investigator to ensure that all relevant information is completed within 1 (Initial Fatal/Life-Threatening or follow up Fatal/Life-Threatening) or 5 (other serious initial and follow up) calendar days if there is an SAE associated with the medication error (see Section 8.3.2) and within 30 days for all other medication errors.

The definition of a Medication Error can be found in Appendix B.

8.4.5 Management of study drug - related toxicities, dose interruptions and dose reductions

Toxicity observed during the course of the study could be managed by interruption of the dose of study treatment or dose reductions. Repeat dose interruptions are allowed as required, for a maximum of 4 weeks on each occasion. If the interruption is any longer, the study team must be informed. Study treatment can be dose reduced to 250 mg twice daily as a first step and to 200 mg twice daily as a second step. If the reduced dose of 200 mg twice daily is not tolerable, no further dose reduction is allowed and study treatment should be discontinued.

Once dose is reduced, escalation is not permitted.

8.4.5.1 Management of haematological toxicity

Management of anaemia

Table 7 Management of Anaemia

Haemoglobin	Action to be Taken
Hb < 10 but \geq 8 g/dl (CTCAE Grade 2)	Give appropriate supportive treatment and investigate causality. Investigator judgement to continue olaparib with supportive treatment (eg transfusion) or interrupt dose for a maximum of 4 weeks. If repeat Hb < 10 but \geq 8 g/dl, dose interrupt (for max of 4 weeks) until Hb \geq 10 g/dl and upon recovery dose reduction to 250 mg twice

	daily as a first step and to 200 mg twice daily as a second step may be considered.
Hb < 8 g/dl (CTCAE Grade 3)	Give appropriate supportive treatment (e.g. transfusion) and investigate causality. Interrupt olaparib for a maximum of 4 weeks, until improved to Hb \geq 10 g/dl. Upon recovery dose reduce to 250 mg twice daily as a first step and to 200 mg twice daily as a second step in the case of repeat Hb decrease

Common treatable causes of anaemia (e.g., iron, vitamin B12 or folate deficiencies and hypothyroidism) should be investigated and appropriately managed. In some cases, management of anaemia may require blood transfusions. For cases where subjects develop prolonged haematological toxicity (\geq 2-week interruption/delay in study treatment due to CTC grade 3 or worse anaemia and/or development of blood transfusion dependence), refer to Section 8.4.5.3 for the management of this.

8.4.5.2 Management of neutropenia, leukopenia and thrombocytopenia

Table 8 Management of neutropenia, leukopenia and thrombocytopenia

Toxicity	Study treatment dose adjustment
CTCAE Grade 1-2	Investigator judgement to continue treatment or if dose interruption, this should be for a maximum of 4 weeks; appropriate supportive treatment and causality investigation
CTCAE Grade 3-4	Dose interruption until recovered to CTCAE gr 1 or better for a maximum of 4 weeks. If repeat CTCAE grade 3-4 occurrence, dose reduce to 250 mg twice daily as a first step and 200 mg twice daily as a second step

Adverse event of neutropenia and leukopenia should be managed as deemed appropriate by the investigator with close follow up and interruption of study drug if CTC grade 3 or worse neutropenia occurs.

Primary prophylaxis with Granulocyte colony-stimulating factor (G-CSF) is not recommended, however, if a subject develops febrile neutropenia, study treatment should be stopped and appropriate management including G-CSF should be given according to local hospital guidelines. Please note that G-CSF should not be used within at least 24 h (7 days for pegylated G-CSF) of the last dose of study treatment unless absolutely necessary.

Platelet transfusions, if indicated, should be done according to local hospital guidelines.

For cases where subjects develop prolonged haematological toxicity (\geq 2 weeks interruption/delay in study treatment due to CTC grade 3 or worse), refer to Section 8.4.5.3.

8.4.5.3 Management of prolonged hematological toxicities while on study treatment

If a subject develops prolonged haematological toxicity such as:

- ≥ 2 weeks interruption/delay in study treatment due to CTC grade 3 or worse anaemia and/or development of blood transfusion dependence
- ≥ 2 weeks interruption/delay in study treatment due to CTC grade 3 or worse neutropenia (ANC $< 1 \times 10^9/L$)
- ≥ 2 weeks interruption/delay in study treatment due to CTC grade 3 or worse thrombocytopenia and/or development of platelet transfusion dependence (Platelets $< 50 \times 10^9/L$)

Check weekly differential blood counts including reticulocytes and peripheral blood smear. If any blood parameters remain clinically abnormal after 4 weeks of dose interruption, the subject should be referred to haematologist for further investigations. Bone marrow analysis and/or blood cytogenetic analysis should be considered at this stage according to standard haematological practice. Study treatment should be discontinued if blood counts do not recover to CTC gr 1 or better within 4 weeks of dose interruption.

Development of a confirmed myelodysplastic syndrome or other clonal blood disorder should be reported as an SAE and full reports must be provided by the investigator to AstraZeneca Patient Safety. Olaparib treatment should be discontinued if subject's diagnosis of MDS and/or AML is confirmed.

8.4.6 Management of Non – hematological toxicity

Repeat dose interruptions are allowed as required, for a maximum of 4 weeks on each occasion. If the interruption is any longer than this the study monitor must be informed. Where toxicity reoccurs following re-challenge with study treatment, and where further dose interruptions are considered inadequate for management of toxicity, then the subject should be considered for dose reduction or must permanently discontinue study treatment.

Study treatment can be dose reduced to 250 mg bd as a first step and to 200 mg bd as a second step. Treatment must be interrupted if any NCI-CTCAE grade 3 or 4 adverse event occurs which the investigator considers to be related to administration of study treatment.

8.4.6.1 Management of new or worsening pulmonary symptoms

If new or worsening pulmonary symptoms (e.g., dyspnoea) or radiological abnormalities occur in the absence of a clear diagnosis, an interruption in study treatment dosing is recommended and further diagnostic workup (including a high - resolution CT scan) should be performed to exclude pneumonitis.

Following investigation, if no evidence of abnormality is observed on CT imaging and symptoms resolve, then study treatment can be restarted, if deemed appropriate by the investigator. If significant pulmonary abnormalities are identified, these need to be discussed with the Study Physician.

8.4.6.2 Management of nausea and vomiting

Events of nausea and vomiting are known to be associated with olaparib treatment. In study D0816C00019 nausea was reported in 71% of the olaparib treated patients and 36% in the placebo treated patients and vomiting was reported in 34% of the olaparib treated patients and 14% in the placebo treated patients (Ledermann JA , et al, 2016). These events are generally mild to moderate (CTCAE grade 1 or 2) severity, intermittent and manageable on continued treatment. The first onset generally occurs in the first month of treatment for nausea and within the first 6 months of treatment for vomiting. For nausea, the incidence generally plateaus at around 9 months, and for vomiting at around 6 to 7 months.

No routine prophylactic anti-emetic treatment is required at the start of study treatment. However, subjects should receive appropriate anti-emetic treatment at the first onset of nausea or vomiting and as required thereafter, in accordance with local treatment practice guidelines. Alternatively, olaparib tablets can be taken with a light meal/snack (i.e., 2 pieces of toast or a couple of biscuits).

As per international guidance on anti-emetic use in cancer subjects, generally a single agent antiemetic should be considered e.g. dopamine receptor antagonist, antihistamines or dexamethasone (National Comprehensive Cancer Network, 2018a, 2018b).

8.4.6.3 Interruptions for intercurrent non-toxicity related events

Study treatment dose interruption for conditions other than toxicity resolution should be kept as short as possible. If a subject cannot restart study treatment within 4 weeks for resolution of intercurrent conditions not related to disease progression or toxicity, the case should be discussed with AZ study physician.

All dose reductions and interruptions (including any missed doses), and the reasons for the reductions/interruptions are to be recorded in the eCRF.

Study treatment should be stopped at least 3 days prior to planned surgery. After surgery study treatment can be restarted when the wound has healed. No stoppage of study treatment is required for any needle biopsy procedure.

Study treatment should be discontinued for a minimum of 3 days before a subject undergoes radiation treatment. Study treatment should be restarted within 4 weeks as long as any bone marrow toxicity has recovered.

Because the AEs related to olaparib may include asthenia, fatigue and dizziness, subjects should be advised to use caution while driving or using machinery if these symptoms occur. For the dose reduction schedule, please refer to Table 5: Dose Reduction Schedule

8.5 Pharmacokinetics

PK parameters are not evaluated in this study.

8.6 Pharmacodynamics

Pharmacodynamic parameters are not evaluated in this study.

8.6.1 Collection of samples

Pharmacodynamic samples will not be taken during the study

8.7 Genetics

No genetic tests will be performed as a part of this study.

8.8 Biomarkers

Biomarkers are not evaluated in this study.

8.9 Medical Resource Utilization and Health Economics

Health Economics/Medical Resource Utilization and Health Economics parameters are not evaluated in this study.

9. STATISTICAL CONSIDERATIONS

9.1 Statistical hypotheses

There is no formal sample size calculation as this study is being conducted as a regulatory requirement for a phase IV study including Indian subjects in the approved indications post marketing of olaparib. The primary endpoint is to demonstrate the safety profile of olaparib in routine clinical practice as assessed by the incidence of AEs (serious and non-serious) observed during trial.

9.2 Sample size determination

Based on the results of OlympiAD and SOLO – 2 trials of Olaparib tablets in platinum sensitive, relapsed ovarian cancer patients with BRCA1/2 mutation and in gBRCAm positive metastatic breast cancer, the incidence rate of the any adverse event (mentioned as part of the labelling information of Olaparib) of severity grade 3 or higher was observed to be approximately 40%. This value of the incidence rate of interest has been used for the sample size estimation in this study.(Pujade-Lauraine et al., 2017; Robson et al., 2017)

Assuming the true incidence rate of any adverse event (mentioned as part of the labelling information of Olaparib) of severity grade 3 or higher to be 40%, corresponding data from approximately 190 Indian adult patients satisfying the protocol specified eligibility criteria will be required in this study for estimating the sample (study based) incidence rate with 7% error margin and using 95% confidence interval. In this study, we expect to recruit 160 patients from platinum sensitive relapsed ovarian cancer and 40 patients from gBRCAm positive metastatic breast cancer as per the Indian HA approved indication to satisfy the Lynparza MA conditional approval.

9.3 Populations for analyses

For purposes of analysis, the following populations are defined:

Population	Description
Enrolled	All subjects who sign the ICF
Evaluable	All enrolled subjects
Safety analysis set	All subjects randomly assigned to Study treatment and who take at least 1 dose of study drug.

9.4 Statistical analyses

Analyses will be performed by AstraZeneca or its representatives. A comprehensive statistical analysis plan will be developed and finalised before database lock and will describe the subject populations to be included in the analyses, and procedures for accounting for missing, unused, and spurious data. This section is a summary of the planned statistical analyses of the primary and secondary endpoints. Any deviations from this plan will be reported in the clinical study report.

9.4.1 Efficacy analyses

No efficacy analyses will be performed on the subjects enrolled in this study.

9.4.2 Safety analyses

Safety analyses will be performed on the safety analysis set as described above in section 9.3.

Data will be summarized using descriptive statistics. Continuous variables will be summarized using the number of observations, mean, standard deviation (SD), median, and range as appropriate. Categorical values will be summarized using the number of observations and percentages as appropriate.

AEs (both in terms of MedDRA preferred terms and CTCAE grade) will be listed individually by subject. Any AE occurring before treatment with olaparib will be included in the data listings but will not be included in the summary tables of AEs.

Any AE occurring within 28 days of discontinuation of study drug (i.e., the last dose of olaparib) will be included in the AE summaries. Any events in this period that occur after a subject has received further therapy for cancer (following discontinuation of olaparib) will be flagged in the data listings.

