Only subjects who discontinue treatment with olaparib before end of Treatment Phase on study will be followed for 28 days after discontinuation of study drug or until the start of alternate treatment intervention, whichever is earlier. A telephone follow-up will be conducted 28 days after the EOT Visit. This will be considered as End-of-Study visit. Every effort should be made to conduct the telephone End-of-Study Visit before the subject starts subsequent treatment. For Follow – Up Phase visit, a window of \pm 3 days will be allowed.

Table 1 Study of Assessments

Study Phase	Screening Phase ^(a)	Treatment Phase					Follow-up Phase						
		On Treatment			EOT	EOS							
Cycle	1	2	3	4	5- 7	8	9						
Visit No.	1	2	3	4	5- 7	8	9						
Study Days	-6 to 0	1 (± 3 days)	15 (± 3 days)	29 (± 3 days)	57, 85 & 141 (± 3 days)	182 (± 3 days)	28 days post-EOT (± 3 days)						
Screening/Enrolment visit													
Informed consent ^(b)	Subjects must sign the informed consent form before any study-specific procedures are performed.												
Eligibility criteria	X												
Demographics/ Review medical history (including all treatments for ovarian cancer/breast cancer)	X												
WHO Performance Status	X			X	X	X	X						
General physical examination	X	Targeted physical exam (based on symptoms)											
Prior concomitant medication recording	Continuous from time of ICF until 28 days after last olaparib dose in treatment phase.												
Study drug administration													
Olaparib dosing	The recommended dose is 300 mg (150 mg X 2 tablets) twice a day												
Disease evaluations (disease characteristics will be performed as per routine clinical practice)													
Disease characteristics assessment	X			X	X								
Tumor imaging	X					X							

Study Phase	Screening Phase ^(b)	Treatment Phase					Follow-up Phase
		On Treatment			EOT	EOS	
Visit No.	1	2	3	4	5-7	8	9
Study Days	-6 to 0	1	15 (± 3 days)	29 (± 3 days)	57, 85 & 141 (± 3 days)	182 (± 3 days)	28 days post-EOT (± 3 days)
Safety evaluations							
Physical examination	X	Symptom-directed physical examination only					
Vital sign parameters	X	X			X	X	
ECG	X	Performed if clinically indicated					
Adverse event monitoring	Continuous from time of ICF until 28 days after last olaparib dose in Treatment Phase and Follow-up Phase if eligible.						
Haematology & Biochemistry ^[c]	X	X	X	X	X	X	X
Hepatitis B and C	X						
Pregnancy Test	X	X	X	X	X	X	X
PT/INR	X	X	X	X	X	X	X

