4. STUDY DESIGN

4.1 Overall design

This is a prospective, single - arm, multicentre, interventional phase – IV trial investigating the safety of olaparib in Indian adult subjects receiving olaparib as per the local approved prescribing information. The investigator will be trained on the locally approved prescribing information before the enrolment of the first subject at their site to ensure compliant and proper dosing of the study drug.

The decision of subjects to participate in this study must not, in any way, impact upon the standard of care that they are receiving or any benefits to which they are otherwise entitled. Prior to data collection, all subjects must sign an informed consent form (ICF) allowing data collection and source data verification in accordance with local requirements and sponsor policy. Subjects who are prescribed olaparib by an independent clinical judgement of investigator in his/her routine practice based on locally approved prescribing information will be eligible for screening under this study. To enrol approximately 200 subjects (160 patients to be enrolled in the ovarian cancer indication and 40 from the breast cancer indication), it is expected that approximately 225 subjects (180 patients with ovarian and 45 patients with breast cancer) will be screened.

Subjects will be monitored throughout the study period for AEs of olaparib.

Subject participation will include a Screening/Enrolment Phase, a Treatment Phase, and a Follow-up Phase. The Screening/Enrolment Phase will be up to 7 days prior to Day 1. The Treatment Phase will extend from Day 1 to Day 182; or until study drug discontinuation due to either disease progression or unacceptable toxicity; or other reasons as listed in Drug Discontinuation Section, whichever occurs first. The Follow-up Phase will begin once a subject discontinues study drug during Treatment Phase, and will continue until 28 days after last dose, death, loss to follow - up, consent withdrawal for study participation, or study end, whichever occurs first (see section 7). Subjects who are observed to continue to receive clinical benefit from olaparib at end of Treatment

Phase (as defined in SoA) will continue treatment in Extension Phase (defined in section 6.7) as long-term clinical benefit is observed or until the investigator decides it is not in the best interest of the subject to continue olaparib treatment.

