7.1.2 Procedures for discontinuation of study treatment

The investigator should instruct the subject to contact the site before or at the time if Study treatment is stopped. A subject that decides to discontinue Study treatment will always be asked about the reason(s) and the presence of any AEs. The date of last intake of Study treatment should be documented in the eCRF. All Study treatment should be returned by the subject at their next on-site study visit or unscheduled visit. Subjects permanently discontinuing Study treatment should be given locally available standard of care therapy, at the discretion of the Investigator.

Discontinuation of Study treatment, for any reason, does not impact on the subject's participation in the study. The subject should continue attending subsequent study visits and data collection should continue according to the study protocol. If the subject does not agree to continue in-person study visits, a modified follow-up must be arranged to ensure the collection of endpoints and safety information. This could be a telephone contact with the subject at 28 days post discontinuation

(End of Study Visit as described in SoA), a contact with a relative or treating physician, or information from medical records. The approach taken should be recorded in the medical records. A subject that agrees to modified follow-up is not considered to have withdrawn consent or to have withdrawn from the study.

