8.3.2 Time - period and frequency for collecting AE and SAE information

Adverse Events will be collected continuously from time of ICF until 28 days after last olaparib dose in Treatment Phase and Follow-up Phase.

All SAEs will be recorded and reported to the sponsor or designee within 24 hours, as indicated in Appendix B. The investigator will submit any updated SAE data to the sponsor within 24 hours of it being available.

Investigators are not obligated to actively seek AE or SAE in former study subjects. However, if the investigator learns of any SAE, including a death, at any time after a subject's last visit and he/she considers the event to be reasonably related to the Study treatment or study participation, the investigator may notify the sponsor.

The method of recording, evaluating, and assessing causality of AE and SAE and the procedures for completing and transmitting SAE reports are provided in Appendix B.

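### Section 9.4.2 counts adverse events that start after further cancer therapy in the olaparib AE summaries, and the protocol conflicts on whether such events are collected

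*Protocol*

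**What the plan says.** Section 9.4.2 sets the counting rule: "Any AE occurring within 28 days of discontinuation of study drug (i.e., the last dose of olaparib) will be included in the AE summaries". It then turns to the part of that window after the next treatment begins, where the only action is on the listings: "Any events in this period that occur after a subject has received further therapy for cancer (following discontinuation of olaparib) will be flagged in the" … No exclusion, censoring or separate tabulation follows. The same section does separate listings from summary tables for events before olaparib, which are listed but kept out of the AE tables.

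Section 7.1.2 makes further therapy likely: "Subjects permanently discontinuing Study treatment should be given locally available standard of care therapy, at the discretion of the Investigator". It states no minimum delay. Section 1.1 tries to get the last contact in first: "Every effort should be made to conduct the telephone End-of-Study Visit before the subject starts subsequent treatment". That call is due 28 days after the End-of-Treatment Visit.

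On collection, Section 8.3.2 says: "Adverse Events will be collected continuously from time of ICF until 28 days after last olaparib dose in Treatment Phase and Follow-up Phase". The overview in Section 4.1 says the Follow-up Phase "will continue until 28 days after last dose, death, loss to follow - up, consent withdrawal for study participation, or study end", whichever is first. The follow-up paragraphs in Sections 1.1 and 4.1 instead stop following early discontinuers at 28 days or when another treatment begins, if that is sooner.

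**The concern.** The primary endpoint (Sections 3 and 9.1) is the number and proportion of subjects with AEs and SAEs. There is no control arm, so the summary proportions themselves will be taken as olaparib's safety profile in Indian patients. While a subject takes study drug, Section 6.5.1 prohibits other anti-cancer therapy. In the 28 days after the last dose such therapy is expected. A first grade 3 or higher event caused by the next regimen would then count as an event in the olaparib summary, and only a reader working through subject listings could see it. Any such effect raises the reported incidence. The conflict over collection adds a second problem: sites following different passages would contribute different amounts of this follow-up to the same table.

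**Working it through.** **The plan's own figure.** Section 9.2 assumes a grade 3 or higher rate of 40%, a margin of 7 points and a 95% interval: n = 1.96² × 0.40 × 0.60 / 0.07² = 188.15, rounded up to 189. The protocol states approximately 190, so the figure reproduces. At the 200 planned, the half-width is 1.96 × √(0.24/200) = 6.8 points. The issue here does not affect the sample size.

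**Do flagged events leave the summaries?** No. The inclusion sentence covers any AE in the window, and the next sentence acts on listings only.

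**Are the events collected?**

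| Place in protocol | Does new therapy end follow-up or collection? |
|---|---|
| Section 1.1, Follow-Up Phase | Yes, if before 28 days |
| Section 4.1, Follow-Up Phase | Yes, if before 28 days |
| Section 4.1, overview of phases | Not listed as a stop |
| Section 8.3.2 and Table 1, AE monitoring | No, 28 days after last dose |
| Section 9.4.2 | No, presupposes such events exist |

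Section 4.1 therefore disagrees with itself.

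**How many subjects could reach this situation?** Day 182 is 182/30.4375 = 5.98 months. With exponential progression (an assumption), the share progressing is 1 − 2^(−5.98/median), using the medians in Sections 2.1 and 4.2:

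- Ovarian, SOLO2 median 19.1 months: 19.5%, or 31.2 of 160.
- Ovarian, Study 19 median 8.4 months: 38.9%, or 62.3 of 160.
- Breast, OlympiAD median 7 months: 44.7%, or 17.9 of 40.

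The total D is 31.2 + 17.9 = 49.1 to 62.3 + 17.9 = 80.2 of 200 (25% to 40%).

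**Shift in the grade 3 or higher rate.** Let s be the share of these subjects who start new therapy inside the window, and q the chance of a grade 3 or higher event in the overlap. Only the 60% without an earlier event can add to the count. Extra subjects = D × s × 0.60 × q; shift = extra / 200. The protocol gives neither s nor q, so both are assumed.

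| D | s | q | Extra subjects | Shift (points) |
|---|---|---|---|---|
| 49.1 | 25% | 5% | 0.4 | 0.2 |
| 49.1 | 50% | 15% | 2.2 | 1.1 |
| 80.2 | 50% | 15% | 3.6 | 1.8 |
| 80.2 | 75% | 25% | 9.0 | 4.5 |

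**An anchor for q.** Section 2.1 gives 50.5% grade 3 or higher events on standard chemotherapy in OlympiAD. Spread at constant hazard over that arm's 4.2-month median PFS (a stand-in for time on treatment), the hazard is −ln(0.495)/4.2 = 0.167 per month. A 14-day overlap (0.46 months) gives q = 1 − exp(−0.167 × 0.46) = 7.4%. With s = 50%, extra subjects are 49.1 × 0.5 × 0.60 × 0.074 = 1.1 to 80.2 × 0.5 × 0.60 × 0.074 = 1.8, or 0.5 to 0.9 points. Toxicity concentrated early in the next regimen would raise this.

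Putting the full 50.5% in as q would give 1.9 to 9.1 points for s from 25% to 75%. That applies a whole-course rate to an overlap of at most 28 days and is not a credible estimate.

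**The case against.** Five arguments deserve weight.

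- **The window is legitimate.** Appendix B 1 defines an AE regardless of relatedness, and a fixed period after the last dose catches late olaparib effects. This stands, and it is why the inclusive summary should remain the main one. A reader might infer that olaparib's profile should rest only on events before new therapy. The documents do not support that: such a set drops late olaparib toxicity, and does so selectively in subjects who stopped early.
- **Few events may be collected.** If sites follow the stop at alternate treatment in Sections 1.1 and 4.1, little reaches the tables. This limits the size, but other passages say the opposite, so it does not settle the matter.
- **Attribution is recorded.** Each AE has a yes/no causality rating against study drug, and SAEs are also rated against other medication (Sections 8.3.4 and 8.3.5). That helps interpretation but does not alter all-cause incidence.
- **The size is probably modest.** PFS events include deaths, which lead to no next therapy. Table 1 schedules imaging only at screening and end of treatment, so fewer progressions may be detected early. Section 8.3.7 makes worsening of mandated laboratory values an AE only if serious or the reason for stopping study drug, apart from associated symptoms. The 40% planning rate covers labelled events only. All of this stands.
- **It belongs to the SAP.** Section 9.4 does defer detail to a SAP, which is not shown and could add a split. But Section 9.4.2 is not silent: it states which events enter the summaries. The point concerns a stated rule.

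**Conclusion.** The point holds in a limited form. Under Section 9.4.2, any event collected after further cancer therapy and within 28 days of the last dose counts toward the AE, SAE and grade 3 or higher incidence, distinguished only in listings. The protocol also contradicts itself on whether those events are collected.

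A reader might infer that the primary rate is materially inflated by next-line toxicity, for instance by several points. The documents do not support that. They give neither the number of subjects starting new therapy within 28 days nor their event risk. With s from 25% to 75% and q from 5% to 25%, the shift is about 0.2 to 4.5 points; the anchored calculation and the limits above make something near 1 point plausible. All of these stay inside the planned 7-point margin. The analysis is descriptive, with no hypothesis test, and the sample size is unaffected. This is a cheap improvement to the primary tables, not a flaw that undermines the study.

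**What to change.** 1. Keep the summary of all AEs to 28 days after the last dose as the main, inclusive analysis.
2. Add to Section 9.4.2 a parallel summary of overall AE, SAE and grade 3 or higher incidence, restricted to events with onset before the first dose of subsequent cancer therapy or up to 28 days after the last olaparib dose, whichever comes first. State that the two are interpreted together. The flag already required identifies the events.
3. Reconcile the follow-up paragraphs of Sections 1.1 and 4.1 with the Section 4.1 overview, Section 8.3.2, Table 1 and Section 9.4.2, so that one rule states whether AE collection stops at new therapy. If it does stop there, the inclusive summary no longer covers the full 28 days for those subjects, and Section 9.4.2 should say so.

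The cost is one extra set of tables, with no new visits or subjects. The downside is that late olaparib effects first seen after new therapy appear only in the inclusive set, which is why it stays the main one.
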